### **Supportive and sensitivity analyses for key secondary endpoints**

To support the analysis for the new onset of diabetes endpoint, the criteria defining new onset will be presented, the diagnostic values causing diagnosis summarized and sensitivity analyses conducted based on each criterion alone.

The three pooled canakinumab doses will be compared to placebo on the key secondary endpoints. Additionally, comparisons between the canakinumab doses will also be reported using the pre-specified log-rank test with hazard ratios reported based on Cox regression.

Additionally, Kaplan-Meier plots will be provided separately for each of the followings:

- Time to adjudication committee confirmed new onset of type 2 diabetes among those with normoglycemic at randomization
- Time to adjudication committee confirmed new onset of type 2 diabetes among those with either pre-diabetes or normoglycemic at randomization
- Time to first pre-diabetes among those with normoglycemic at randomization.

The key secondary cardiovascular endpoint will also be analyzed adjusting for the same covariates used for the covariate adjusted analysis of the primary variable.

The key secondary endpoint new onset of diabetes will also be supported by analyses using data from the study's washout period. These analyses will be defined in a separate analysis

plan for the washout period and will be reported in a separate study report or addendum to the main study report.

### **6.3.3 Other secondary efficacy variables**

[figure not shown]
As stated in [section 6.1.3](#) all-cause mortality is considered a very important secondary endpoint due to its importance as both an efficacy and safety outcome, but it is not part of the pre-specified testing procedure for primary and key secondary endpoints, because given the expected number of deaths in the trial it would not have been possible to adequately power the key secondary mortality endpoint.

[figure not shown]
All-cause death and the composite of all-cause death, stroke or MI will be analyzed on the FAS and PPS1 with a log-rank test stratified by time since index MI and trial part. The hazard ratios will be estimated using a Cox regression model stratified by time since index MI and trial part.

[figure not shown]
Kaplan-Meier plots showing each treatment will be provided both overall and by trial part. Patients who did not die will be considered censored at the last time they were reported to be alive.

[figure not shown]
These secondary endpoints will also be analyzed adjusting for the same covariates used for the covariate adjusted analysis of the primary variable.

[figure not shown]
The three pooled canakinumab doses will be compared to placebo on the other secondary endpoints. Additionally, comparisons between the canakinumab doses will also be reported.

[figure not shown]

[figure not shown]

[figure not shown]

[figure not shown]

[figure not shown]

[figure not shown]

## 6.4 Kaplan-Meier type analyses and graphs

Because this trial has two consecutively recruited trial parts with different allocation ratios that may differ in important predictive covariates and since one treatment group is not even represented in trial part 1, simply pooling data across trial parts to produce an overall Kaplan-Meier graph would not be appropriate. For this reason an alternative approach for producing such a Kaplan-Meier type graph is described in [section 6.4.1](#) below. Such graphs and within any trial part Kaplan-Meier plots will follow the general principles described in [section 6.4.2](#).

Kaplan-Meier type analyses and plots will be provided (including by trial part) for the primary endpoint, key secondary endpoints, secondary endpoints and [REDACTED]

### 6.4.1 Overall Kaplan-Meier type graphs across trial parts

A Cox model stratified for treatment group (placebo, 50 mg, 150 mg or 300 mg) and time since index MI (< 6 months, ≥ 6 months), with trial part as a covariate will be used to obtain Breslow estimates ([Breslow 1974](#)) for the predicted survival curves for each combination of treatment group, time since index MI and trial part – including for the 50 mg group in trial part 1. These predicted survival curves will then be aggregated for an appropriate cohort of patients within each of the 4 treatment groups to obtain a single overall Kaplan-Meier type graph for the 4 treatment groups.

The use of a Cox model stratified for treatment group (placebo, 50 mg, 150 mg or 300 mg) – and also time since index MI (< 6 months, ≥ 6 months) – is a suggestion by Zhang et al. ([Zhang et al. 2007](#)) and [name] ([personal communication, 2011](#)). As pointed out by Zhang et al. such a model makes no assumption of proportional hazards between treatment groups or time since index MI groups. Thus, it is more appropriate for obtaining a graphical representation that allows an inspection of the relative effectiveness of treatment groups over time. Using trial part as a covariate and assuming the same proportional effect of trial part for the whole follow-up period for each of the 8 strata (treatment group / time since index MI)

allows extrapolation of what a 50 mg group in trial part 1 would have been like, as suggested by [name] ([personal communication, 2011](#)). To assess the assumptions involved the predicted survival curves from this model for the placebo, 150 mg and 300 mg groups in each stratum and for the 50 mg group in all trial part 2 strata will be compared graphically to those from a model that treats trial part as an additional stratification variable. Should the assumption be strongly violated with respect to trial part having a constant effect over time, it would be an alternative to assume a trial part effect that is only proportional over specific time intervals (e.g. up to 90 days, day 91 to day 183, days 184 to 1 year, 1 year to 2 years, > 2 years).

The overall aggregated cohort survival estimate will be obtained from the estimates for each treatment group / time since index MI / trial part combination using the Hakulinen method ([Hakulinen 1982](#)). Compared with the more simple Ederer method this is expected to more closely reflect what might have been obtained, if this study had been conducted with 4 treatment arms from the start. The reason is that the follow-up time after which administrative censoring at trial end will occur will differ – by design – between the trial parts ([Thomsen et al. 1992](#)) ([Therneau and Grambsch 2000, pp. 261-287](#)).

The cohort for which the cumulative failure rate is estimated using the Hakulinen method will be constructed so that within each trial part the distribution of time since index MI and distribution of maximal potential follow-up is the same for each treatment group. To achieve this within each trial part

1. All the patients in all treatment groups and time since index MI strata in that trial part are selected.
2. Their length of follow-up  $F_i$  and time since index MI information is retained.
3. These patients are assumed to be the (identical) hypothetical recruited cohorts for each of the four treatment groups.

Note that the length of follow-up  $F_i$  is taken to be

- for those patients that were censored: the time from randomization to the maximum actual follow-up for CV events (not just for the first event)
- for patients that had a non-fatal version of the endpoint of interest (e.g. non-fatal MI in case of analyzing the primary MACE endpoint) the same approach as for those patients that were censored will be used
- for patients that had a fatal version of the endpoint of interest (e.g. fatal MI in case of analyzing the primary MACE endpoint) the maximum potential follow-up will be used, i.e. the time from randomization to the maximal potential follow-up date, defined to be the analysis cut-off date (see [Section 2.3.7](#)).

For each patient  $i$  let  $S_i(t)$  be the estimated survival curve based on that patient's treatment group, time since index MI and trial part. If patients are ordered from shortest to longest possible follow-up time  $F_{(1)}, F_{(2)}, \dots, F_{(k)}$ , then the Hakulinen estimate ([Hakulinen 1982](#)) for the cumulative survival function  $S(t)$  is calculated recursively for any  $F_{(k)} < t \leq F_{(k+1)}$  as

$$S(t) = S(F_{(k)}) \times \left[ \sum_{i=1, \dots, n} S_i(t) \times \mathbf{1}\{F_i > t\} \right] / \left[ \sum_{j=1, \dots, n} S_j(F_{(k)}) \times \mathbf{1}\{F_j > F_{(k)}\} \right]$$

as described by Thomsen et al. ([Thomsen et al. 1992](#)), Nielsen ([Nielsen 1997](#)) and Therneau and Grambsch ([Therneau and Grambsch 2000, pp. 261-287](#)).

Note that valid confidence intervals cannot be obtained for these estimates in a straightforward fashion, because of the artificially inflated “apparent sample size” resulting from the way in which the algorithm above ensures balanced time since index MI/trial part across treatment groups and censoring patterns. If pointwise confidence intervals are required (e.g. primary and secondary endpoints) one could create e.g.  $B=2,000$  bootstrap samples, repeat the whole process above (starting from fitting the Cox model) for each bootstrap sample and then obtain interval percentile (or BCa) Bootstrap confidence intervals as described by Efron and Tibshirani (Efron and Tibshirani 1993, pp. 170-176 and pp. 184-188) e.g. for times  $t=1$  year, 2 years, 3 years and 4 years. algorithm might be applied.

#### 6.4.2 Kaplan-Meier graphs for each trial part and general principles

The approach for Kaplan-Meier graphs closely follows the recommendations by Pocock et al. (2002).

Cumulative event rate estimates ( $1 -$  estimated survivor function) in % versus time of follow-up in years will be shown based on Kaplan-Meier estimates. Compared to showing the survivor function this maximizes detail without needing a break in the scale.

While “technically, any survival plot can be extended right through to the longest follow-up time” as Pocock et al. point out “this extension is not good statistical practice, since for any such plot the eye is drawn to the right (i.e. where the plot finishes), which is where there is least information and greatest uncertainty”. Kaplan-Meier curves will therefore only drawn up to the time at which the total population at risk for the event in question has decreased to 10% of the size of the analysis set. This matches the recommendation by Pocock et al. who wrote that they “[...] recommend that survival plots be halted once the proportion of patients free of an event, but still in follow-up, becomes unduly small. [...] What constitutes “unduly small” is open to debate and depends on the context. It will often be reasonable to curtail the plot when only around 10–20% are still in follow-up.” As CANTOS is a large outcome trial the lower end of this range (10%) will be used.

For the kind of Kaplan-Meier type graphs described in section 6.4.1 above, this will be taken to mean that the graph will be truncated at the length of follow-up achieved by 10% of patients across all trial arms and trial parts. This means that the graph for the 50 mg dose will be continued somewhat past the point up to which 10% of 50 mg patients were followed up.

The number of patients at risk in each group will be displayed below the x-axis at year=0, 1, 2, 3... and each subsequent year of follow-up to provide information on the extent of follow-up. Pointwise 95% confidence intervals at each full year may be shown if feasible. In line with the recommendations by Pocock et al. this provides some measure of statistical uncertainty and ensures that any visual signs of treatment differences do not look more convincing than they really are. Results of inferential statistics (e.g. primary model-based hazard ratios, 95% confidence intervals and p-value for primary endpoint) will also be shown on the figure. Kaplan-Meier tabulations will show number at risk, number failed, cumulative number failed, cumulative number censored, Kaplan-Meier estimates of failure rate with pointwise 95% confidence intervals. Similar tabulations will be provided by time interval also including the estimated hazard at interval midpoint.

It is recognized that just as discussed by Pocock et al. caution is needed in interpreting the shape of survival plots in particular due to the lack of any pre-specified hypothesis about its shape and the lack of statistical power to explore subtleties of treatment difference other than the overall comparison.

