#### **Time-to-event variables**

Regarding time-to-event variables only observed/reported events will be used in the analysis – i.e. events will not be imputed for censored patients, except for specific sensitivity analyses. This means that in the primary analysis censoring of non-observed events will be assumed to be non-informative. Incomplete dates of events and censoring dates will be imputed as described below.

In the primary analysis, all patients, including those who discontinue study therapy due to lack of efficacy, adverse events or abnormal laboratory values, will be followed until death or the end of the study. Information on patients discontinuing study drug or participation in trial visits will be collected whenever possible and will be used in the analysis.

In general, every effort will be made to collect information about the primary outcome events for those patients who discontinued treatment or their participation in the trial. In patients who could not be followed up for primary outcome events, it is aimed to at least determine the vital status of the patients at the final visit.

The following rules will be applied separately for the composite MACE endpoint and for all its individual components. Patients who have not experienced the respective endpoint will be censored on the date of the last follow-up defined as the earliest of:

- the date of death unless the patient withdrew his consent for the collection of follow-up information,
- the date of the last visit satisfying at least one of the following:
  - yes to the question of “indicates if the subject attended the scheduled visit” on the Visit Information CRF
  - yes/no to the question of “any clinical events since last visit” on the Visit Information CRF

- yes/no to the top three questions (death, myocardial infarction, stroke) on the Clinical Event Tracking CRF.

Should the censoring date lie after the chosen analysis cut-off date, it will be set to the analysis cut-off date. Note that this censoring date should be derived independently of any specific analysis other than all cause mortality, because it will be used to describe the extent of follow-up for (potentially multiple) cardiovascular events and for multiple different time-to-event analyses (e.g. time to MACE, time to MI, analyses of multiple cardiovascular events). For all-cause death, the censoring will occur at the minimum of withdrawal of consent, last known alive date and analysis cut-off date.

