### **Supportive, sensitivity and subgroup analyses for the primary endpoint**

The components of the composite primary efficacy endpoint (CV death, fatal or non-fatal MI, fatal or non-fatal stroke) will also be analyzed individually in order to evaluate their contributions to the overall treatment effect. No adjustment for multiplicity is foreseen for this purpose.

The three pooled canakinumab doses will be compared to placebo on the primary composite endpoint and its components, because in case of similar efficacy on all three doses this would be the most powerful test of the scientific hypothesis addressed by this trial. Additionally, when all three doses have similar efficacy, such a pooled analysis approach may provide the most precise information on the effects in subgroups.

Dose response will be evaluated using the methods discussed in [section 6.5](#). Additionally, comparisons between the canakinumab doses based on the primary model will also be reported.

Kaplan-Meier type analyses will be presented as described in [section 6.4](#) overall and by trial part to summarize the time to first event in the composite endpoint, by presenting the time-dependent cumulative frequency and percentage of patients who reach the primary composite endpoint by treatment group.

Additionally, log time by treatment interaction will be evaluated to identify violations in the proportional hazards assumption, which might indicate a time-varying treatment effect. An Anderson-Darling type test based on a score process (cumulative sum of the Schoenfeld residuals) as recommended by Kvaløy and Neef ([Kvaløy and Neef 2004](#)) will be performed. For each trial arm within each trial part  $-\log(S(\text{time}))$  vs. time and  $\log(-\log(S(\text{time})))$  vs.  $\log(\text{time})$  will be plotted.

To ensure that any unblinding of patients during the double-blind phase had no meaningful impact on the overall study results, a sensitivity analysis of the primary endpoint will be performed by excluding data from all patients who were unblinded during the double blind phase of the study (i.e. all the unblinded patients will be censored at the time of unblinding).

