**Figure 6-5 Closed testing procedure with full details of testing of key secondary endpoints**

This figure as compared to [Figure 6-4](#) shows the full details of the Bonferroni-Holm procedure for the key secondary endpoints in a graphical form, but is otherwise identical in content.

Based on this testing procedure, once the primary null hypothesis for a dose has been rejected the key secondary endpoints for that dose are tested using a weighted Bonferroni-Holm test ([Holm 1979](#)) at the available local significance level for the key secondary endpoints for that dose. The weighting of this Bonferroni-Holm procedure will be 90% for the key secondary CV composite and 10% for the key secondary new onset of diabetes endpoint.

The secondary efficacy variable corresponding to new onset diabetes in patients with pre-diabetes at randomization will be the time from randomization to the first of repeated FPG  $\geq$  126 mg/dL or the first of repeated HbA1c  $\geq$  6.5% or start of new anti-diabetic concomitant medication(s) for glucose lowering purpose. All identified cases of new onset of diabetes will be confirmed by the adjudication committee.

Due to the discrete nature of the visits when new onset of type 2 diabetes can be determined, events identified at the same visit time point as defined in [section 2.3.6](#) for different patients will be considered as tied events and the exact method for handling ties will be used. This assumes that for each of these patients new onset of diabetes occurred at some time point since the previous visit, but that due to the impossibility of continuous monitoring of the patients the true order in which each of them progressed to diabetes is unknown ([Allison 1995](#),

pp. 127 to 137). For this variable patients without new onset of diabetes will be considered censored at the time of their last laboratory assessment. Patients not diagnosed at a regular visit or at the study completion visit will be assigned to one of the scheduled visits as per the algorithm in [section 2.3.6](#).

Subgroup analyses as specified in Table 2-3-1 will be conducted for the key secondary new onset of diabetes endpoint. These will include subgroup analyses by race, which could potentially influence HbA1c levels.

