### 6.4.3 Calculation of number needed to treat

The number needed to treat (to benefit) will be calculated using the method of Altman and Andersen (Altman and Andersen 1999) for each dose for different durations of treatment as

$$\text{NNT (t)} = 1 / [ S_{\text{placebo(t)}}^{\text{hazard ratio for dose versus placebo}} - S_{\text{placebo(t)}} ]$$

using  $S(t)$  calculated as described in section 6.4.1. It will be extrapolated as described by Altman and Andersen to the 5 year timepoint from the timepoint of follow-up achieved by 10% of patients across all trial arms and trial parts  $T_{10\%}$  under the assumption of approximately constant event rates and benefit as

$$\text{NNT (5 years)} = ( T_{10\%} / 5 \text{ years} ) \times \text{NNT (} T_{10\%} \text{)}.$$

3 year and 1 year NNTs will be calculated and it is expected that this can be done without such an extrapolation unless the study is stopped an interim analysis. Confidence intervals with appropriate coverage probabilities will be calculated using Bootstrap methods.

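### New-onset diabetes is reported as 1 minus Kaplan-Meier with death as ordinary censoring, which overstates the percentage of patients who develop diabetes; the NNT shares the feature to a small degree

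*SAP*

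**What the plan says.** **Censoring.** SAP 6.3.2 states for new-onset diabetes: "For this variable patients without new onset of diabetes will be considered censored at the time of their last laboratory assessment". Death has no separate role, so a death without diabetes ends in plain censoring. For MACE, SAP 2.3.9 lists "the date of death unless the patient withdrew his consent for the collection of follow-up information" among the censoring dates and introduces the list with "The following rules will be applied separately for the composite MACE endpoint and for all its individual components".

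**Display.** SAP 6.4 announces that "Kaplan-Meier type analyses and plots will be provided (including by trial part) for the primary endpoint, key secondary endpoints, secondary endpoints"; the rest of that sentence is blacked out. New-onset diabetes is a key secondary endpoint, and SAP 6.3.2 plans its plots overall and by trial part. SAP 6.4.2 defines the plotted quantity as 1 minus the survivor function, in percent, and tabulates "Kaplan-Meier estimates of failure rate with pointwise 95% confidence intervals". For the primary endpoint, SAP 6.3.1 describes the output as the "percentage of patients who reach the primary composite endpoint by treatment group".

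**NNT.** SAP 6.4.3 says "The number needed to treat (to benefit) will be calculated" for each dose. It takes the survival function from SAP 6.4.1 (stratified Cox model, Breslow estimates, Hakulinen aggregation), not from the table in 6.4.2. It names no endpoint.

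**Competing risks.** No visible section specifies a cumulative incidence estimate. The reference list holds a paper on Cox regression for competing risks that no visible text cites.

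**The concern.** With death as a competing event, 1 minus Kaplan-Meier estimates the risk in a hypothetical population in which nobody dies, and only if death is independent of the endpoint. It does not estimate the percentage of randomised patients who reach the endpoint, which is how a reader will take a failure rate in percent. The two differ most for diabetes, because every death competes.

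At stake are the absolute percentages for a key secondary endpoint and their confidence intervals and, to a smaller degree, the NNT. These are the figures used to weigh benefit against risk. Testing is not at stake: the log-rank test and the Cox model compare cause-specific hazards, for which censoring at death is the usual handling.

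**Working it through.** **Inputs from the documents.** Placebo MACE rate 3.25 to 4 per 100 person-years (protocol 9.6). Hazard ratio 0.80 for every dose (protocol 9.6). Pre-diabetes in about 35% of patients (protocol section 4). Allocation 3,333 placebo, 2,253 at 300 mg, 2,253 at 150 mg, 2,160 at 50 mg (protocol 5.2). Deaths of undetermined cause count as cardiovascular (protocol 15.1), so only non-cardiovascular death competes with MACE.

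**Assumptions, because the documents give no figure.** Diabetes 4 (range 3-6), all-cause death 2.5 (range 1.5-3.5) and non-cardiovascular death 0.8-1.6 per 100 person-years; constant hazards.

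**The plan's own figure.** The documents state no cumulative incidence and no NNT to reproduce. Their rate conversion can be checked: in protocol 9.6, 7.2% over 2 years in the cited statin trial gives -ln(1 - 0.072)/2 = 0.037, the stated 3.7 per 100 person-years.

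**Formulas.** With endpoint hazard L and competing hazard M:
- 1 minus Kaplan-Meier tends to 1 - exp(-L t).
- Cumulative incidence is L/(L+M) x [1 - exp(-(L+M) t)].
- NNT is 1 divided by the difference in risk, with 0.8 L on drug.

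**Diabetes, L = 0.04, M = 0.025.**
- 3 years: 1 - exp(-0.12) = 11.31%. Cumulative incidence (0.04/0.065) x [1 - exp(-0.195)] = 10.90%. Gap 0.41 points.
- 5 years: 1 - exp(-0.20) = 18.13%. Cumulative incidence (0.04/0.065) x [1 - exp(-0.325)] = 17.08%. Gap 1.05 points.
- Over the assumed ranges the 5-year gap runs from 0.5 points (diabetes 3, death 1.5) to 2.0 points (diabetes 6, death 3.5).
- Precision: 35% of 3,333 is about 1,167 placebo patients. With follow-up assumed uniform over 3-6 years, the Greenwood standard error at 5 years is about 1.3 points, so the central gap is about 0.8 of a standard error.

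**NNT for MACE, L = 0.04 on placebo and 0.032 on drug, equal non-cardiovascular death in the arms.**

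| Time | Death censored | M = 0.008 | M = 0.016 |
|---|---|---|---|
| 3 years | 46.4 | 47.0 | 47.5 |
| 5 years | 29.9 | 30.5 | 31.1 |

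The excess in the placebo MACE percentage at 5 years is 0.35 to 0.68 points.

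**Direction of the NNT shift.** Take M = 0.02 on placebo, at 5 years. The risk difference with death censored is 3.34 points (NNT 29.9).
- Non-cardiovascular death on drug 0.6 times placebo: cumulative-incidence difference 2.92 points, NNT 34.3.
- Equal: 3.19 points, NNT 31.4.
- 1.3 times placebo: 3.39 points, NNT 29.5.

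The planned NNT is therefore too favourable in the first two cases and slightly too unfavourable in the third.

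**The case against.** **The NNT shift is small against its uncertainty.** This stands. Splitting 1,400 events by allocation and hazard ratio gives 1,400 x 3,333/(3,333 + 0.8 x 6,666) = 538 on placebo and 1,400 x 0.8 x 2,253/8,666 = 291 at 150 mg. The standard error of the log hazard ratio is the square root of (1/538 + 1/291) = 0.073, so a hazard ratio of 0.80 has a 95% interval of about 0.69 to 0.92 and the 5-year NNT one of about 19 to 78. The SAP's extrapolation to 5 years matters as much: starting from 4 years it gives 28.9 instead of 29.9.

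**Five years may lie beyond the data.** This also stands. SAP 6.4.3 expects only the 1-year and 3-year NNT without extrapolation, and at 3 years the diabetes gap is about 0.4 points.

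**The plan has endpoints free of the problem.** True for all-cause mortality and for the composite of MI, stroke and all-cause death, but neither describes diabetes.

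**A competing-risk analysis may sit in blacked-out text.** Possible: parts of SAP 6.3 are redacted and the reference list points that way. It would not change the estimator that SAP 6.4.2 openly specifies.

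**Stronger readings that the documents do not support.** A reader might infer that Kaplan-Meier failure rates are planned for MI, stroke and cardiovascular death separately. SAP 6.3.1 ties that output to the composite, and the visible list in 6.4 does not name the components. A reader might also infer that the NNT is computed from the 6.4.2 table; it uses the 6.4.1 curve.

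**Conclusion.** The point holds for new-onset diabetes. The stated estimator overstates the percentage who develop diabetes whenever deaths occur, by about 0.4 points at 3 years and 1.05 points at 5 years under assumed rates of 4 (diabetes) and 2.5 (death) per 100 person-years. The sign is certain; the size rests on those assumptions and on constant hazards.

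For the NNT the point is minor. The 6.4.1 curve also censors competing death, but if the endpoint is MACE only non-cardiovascular death competes, and the 5-year value moves from 29.9 to about 30.5-31.1 with equal competing death in the arms. It would be tempting to conclude that the plan overstates the benefit of canakinumab. The documents do not support that as a general statement: the direction depends on how the drug affects non-cardiovascular death, which is unknown at the planning stage.

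Log-rank tests, hazard ratios, alpha and power are untouched. The change is worth making because it is cheap and needs no new data.

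**What to change.** - **SAP 6.4.2:** for new-onset diabetes, plot and tabulate within each trial part the Aalen-Johansen cumulative incidence with death as the competing event. State how a death after the last laboratory assessment is dated. Do the same for MI, stroke and cardiovascular death (competing event: death not counted in the endpoint) if their failure rates are shown.
- **SAP 6.4.3:** name the endpoint of the NNT, and add a sensitivity NNT equal to 1 divided by the difference in cumulative incidence. Trial part 2, with about 9,257 of 10,000 patients (protocol 5.2) and all four arms randomised concurrently, would be a simple basis that avoids rebuilding the across-part curve of 6.4.1.
- **Unchanged:** the log-rank tests and Cox hazard ratios.

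The cost is a short SAP amendment and modest programming on data already collected. Reported percentages will be slightly lower.
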